3 NON-UW RESEARCH SETTING

Complete this section only if UW investigators and people named in the SUPPLEMENT: Non-UW Individual Investigators will conduct research procedures outside of UW and Harborview

3.1 Reason for locations. Describe the reason(s) for choosing the locations.

This is especially important when the research will occur in locations or with populations that may be vulnerable to exploitation. One of the three ethical principles the IRB must consider is justice: ensuring that reasonable, non-exploitative, and well-considered procedures are administered fairly, with a fair distribution of costs and potential benefits.

3.2 Local context. Culturally appropriate procedures and an understanding of local context are an important part of protecting subjects. Describe any site-specific cultural issues, customs, beliefs, or values that may affect the research, how it is conducted, or how consent is obtained or documented.

Examples: It would be culturally inappropriate in some international settings for a woman to be directly contacted by a male researcher; instead, the researcher may need to ask a male family member for permission before the woman can be approached. It may be appropriate to obtain permission from community leaders prior to obtaining consent from individual members of a group. In some distinct cultural groups, signing forms may not be the norm.

This federal site maintains an international list of human research standards and requirements:
<http://www.hhs.gov/ohrp/international/index.html>

3.3 Location-specific laws. Describe any local laws that may affect the research (especially the research design and consent procedures). The most common examples are laws about:

- **Specimens** – for example, some countries will not allow biospecimens to be taken out of the country.
- **Age of consent** – laws about when an individual is considered old enough to be able to provide consent vary across states, and across countries.
- **Legally authorized representative** – laws about who can serve as a legally authorized representative (and who has priority when more than one person is available) vary across states and countries.
- **Use of healthcare records** – many states (including Washington State) have laws that are similar to the federal HIPAA law but that have additional requirements.

3.4 Location-specific administrative or ethical requirements. Describe local administrative or ethical requirements that affect the research.

Example: A school district may require researchers to obtain permission from the head district office as well as school principals before approaching teachers or students; a factory in China may allow researchers to interview factory workers but not allow the workers to be paid for their participation.

3.5 If the PI is a student: Does the research involve traveling outside of the US?

	No
	Yes

→ If yes, confirm by checking the box that (1) you will register with the [UW Office of Global Affairs](#) before traveling; (2) you will notify your advisor when the registration is complete; and (3) you will request a UW Travel Waiver if the research involves travel to the [list of countries](#) requiring a UW Travel Waiver.

	Confirmed
--------------------------	-----------

4 RECRUITING and SCREENING PARTICIPANTS

4.1 Recruiting and Screening. Describe how subjects will be identified, recruited, and screened. Include information about: how, when, where, and in what setting. Identify who (by position or role, not name) will approach and recruit subjects, and who will screen them for eligibility.

Note: Per UW Medicine policy, the UW Medicine eCare/MyChart system may not be used for research recruitment purposes.

Recruitment may use one or several of the following methods:

- Social media posts via Facebook, Instagram, Google AdWords and/or NextDoor. Posts will guide potential participants to the IMPACT Study eligibility screening webpage.
- Recruitment flyers posted in community-based pediatric clinics, recreational centers, boys and girls clubs, and elementary schools will have a QR code and weblink directing to the study eligibility screening webpage.
- ITHS Patient cohort identification. We will submit a request to the ITHS biomedical informatics team to assist us with identifying prospective participants from the UW Medicine electronic medical records – search criteria will include child age (7-11 years) with asthma diagnosis ICD9 or ICD10 code. Among

those that fit our criteria, we will request the extracted cohort information include: child name and age, parent name, parent email and home address. We will opt in to the ITHS compliance “add on” such that UW compliance will be notified of all extracted participants. Parents will be contacted by the study team via email and/or direct mailing to include information about the study, a link to the IMPACT study webpage (where parents may choose to complete eligibility screening), and PI contact information (phone, email).

- Institute of Translational Health Sciences “Participate in Research” online webpage <https://www.iths.org/participate/studies/>. A brief description of the study, eligibility, website, and contact information

Screening

Interested potential participants will visit the IMPACT study webpage and complete eligibility screening. The screening will be automatically scored within REDCap and indicate whether participants appear to meet eligibility criteria or not. Those who are not eligible are thanked for their time. Those who are eligible will be advised that the study team will contact them (see recruitment follow-up description) to invite subjects to an in-person data collection session. REDCap uses unique identifiers for potential participants and only the study team has the master list connecting potential participant emails, names, and identifiers.

For prospective participants that have questions, the PI phone and email will be provided on all recruitment materials.

4.2 Recruitment materials.

a. What materials (if any) will be used to recruit and screen subjects?

Examples: talking points for phone or in-person conversations; video or audio presentations; websites; social media messages; written materials such as letters, flyers for posting, brochures, or printed advertisements; questionnaires filled out by potential subjects.

Recruitment flyers, emails, web-postings, social media posts, direct mailings and study webpage will be used to recruit and screen subjects.

b. Upload descriptions of each type of material (or the materials themselves) to **Zipline. If letters or emails will be sent to any subjects, these should include a statement about how the subject’s name and contact information were obtained. No sensitive information about the person (such as a diagnosis of a medical condition) should be included in the letter. The text of these letters and emails must be uploaded to **Zipline** (i.e., a description will not suffice).**

HSD encourages researchers to consider uploading descriptions of most recruitment and screening materials instead of the materials themselves. The goal is to provide the researchers with the flexibility to change some information on the materials without submitting a Modification for IRB approval of the changes. Examples:

- *Provide a list of talking points that will be used for phone or in-person conversations instead of a script.*
- *For the description of a flyer, include the information that it will provide the study phone number and the name of a study contact person (without providing the actual phone number or name). This means that a Modification would not be necessary if/when the study phone number or contact person changes. Also, instead of listing the inclusion/exclusion criteria, the description below might state that the flyer will list one or a few of the major inclusion/exclusion criteria.*
- *For the description of a video or a website, include a description of the possible visual elements and a list of the content (e.g., study phone number; study contact person; top three inclusion/exclusion criteria; payment of \$50; study name; UW researcher).*

4.3 Relationship with participant population. Do any members of the study team have an existing relationship with the study population(s)?

Examples: a study team member may have a dual role with the study population (for example, being their clinical care provider, teacher, laboratory director or tribal leader in addition to recruiting them for his/her research).

	No
	Yes

→ If yes, describe the nature of the relationship.

4.4 Payment to participants. The IRB must evaluate subject payment for the possibility that it will unduly influence subjects to participate. Refer to [GUIDANCE Subject Payment](#) when designing subject payment plans. Provide the following information about your plans for paying research subjects in the text box below or note that the information can be found in the consent form.

- The total amount/value of the payment
- Schedule/timing of the payment [i.e., when will subjects receive the payment(s)]
- Purpose of the payment [e.g., reimbursement, compensation, incentive]
- Whether payment will be “pro-rated” so that participants who are unable to complete the research may still receive some part of the payment

The IRB expects the consent process or study information provided to the subjects to include all of the above-listed information about payment, including the number and amount of payments, and especially when subjects can expect to receive payment. One of the most frequent complaints received by HSD is from subjects who expected to receive cash or a check on the day that they completed a study and who were angry or disappointed when payment took 6-8 weeks to reach them.

Participant dyads (parent and child) will receive graduated incentive payments in the form of digital gift cards:

- \$50 upon completion of the baseline study visit (T0)
- \$100 upon completion of the post-intervention visit (T1)
- \$150 upon completion of the 8-week follow-up visit (T2)

OPTIONAL

Participants will also be given the option to opt-in to completing a child cognitive (executive functioning) battery. This will be indicated as optional on the consent, but is available only to those who have in person visits. Cognitive battery completion will be paid an additional \$25 per timepoint. This additional incentive payment will be a digital gift card.

4.5 Non-monetary compensation. Describe any non-monetary compensation that will be provided. Example: extra credit for students; a toy for a child. If class credit will be offered to students, there must be an alternate way for the students to earn the extra credit without participating in the research.

All families will receive a home spirometry device, which is used to measure lung functioning in children. Families will use this periodically throughout the study but also keep it for future use. Children may also receive stickers or another small token during/following in-person sessions (e.g., bubbles, pencil).

4.6 Will data or specimens be accessed or obtained for recruiting and screening procedures prior to enrollment?

Examples: names and contact information; the information gathered from records that were screened; results of screening questionnaires or screening blood tests; Protected Health Information (PHI) from screening medical records to identify possible subjects.

	No	→ If no, skip the rest of this section; go to question 5.1 .
	Yes	→ If yes, describe the data and/or specimens (including PHI) and whether it will be retained as part of the study data.

Screening information includes:

Parent

- First name, email address, phone number, and preferred mode of contact (text, phone, email) for follow-up.
- Confirmation that parent/child live in King, Pierce, or Snohomish county (if in person visit desired). Those outside of King, Pierce, or Snohomish counties will have a remote visit option.
- Child's primary caregiver residing with the child (50% or more)
- ≥ 18 years
- Speaks/reads English
- Has smartphone with data plan
- Parent-reported asthma responsibility mean score ≤ 2.5 (per screening survey)

Child

- First name, age, confirmation of prescription for daily asthma medication
- NO parent report of conditions that impair the child's ability to learn shared-management including: 1) developmental delay (e.g., language < 5 -year level), 2) comorbid condition (cancer, diabetes, autism); or 3) current asthma exacerbation at the time of recruitment (defined as a prescription for oral corticosteroids) as this is a serious health event and not an opportune time for learning shared management.

Study data will be collected and stored in REDCap database, accessible only to the study team.

4.7 Consent for recruiting and screening. Will consent be obtained for any of the recruiting and screening procedures? ([Section 8: Consent of Adults](#) asks about consent for the main study procedures).

"Consent" includes: consent from individuals for their own participation; parental permission; assent from children; consent from a legally authorized representative for adult individuals who are unable to provide consent.

Examples:

- For a study in which names and contact information will be obtained from a registry: the registry should have consent from the registry participants to release their names and contact information to researchers.
- For a study in which possible subjects are identified by screening records: there will be no consent process.
- For a study in which individuals respond to an announcement and call into a study phone line: the study team person talking to the individual may obtain non-written consent to ask eligibility questions over the phone.

	No	→ If no, skip the rest of this section; go to question 5.1 .
	Yes	→ If yes, describe the consent process.

See uploaded recruitment descriptions.

a. Documentation of consent. Will a written or verifiable electronic signature from the subject on a consent form be used to document consent for the recruiting and screening procedures?

No

→ If no, describe the information that will be provided during the consent process and for which procedures.

Yes, written

→ If yes, and a **written** signature will be used to document consent:

- Upload the consent form to **Zipline**.

Yes, electronic

→ If yes, and an **electronic** signature will be used to document consent:

- Upload the consent form to **Zipline**.
- If the eSignature process or method for recruiting and screening is different than for the main study procedures**, use the questions about electronic consent in Section 8.3 and 8.4 to differentiate between recruiting/screening and main study electronic consent. **If electronic consent will be used for recruiting/screening but not main study consent**, use 8.3 and 8.4 to describe eConsent and note that it is only for recruiting/screening.

5 PROCEDURES

5.1 Study procedures. Using lay language, provide a complete description of the study procedures, including the sequence, intervention or manipulation (if any), drug dosing information (if any), blood volumes and frequency of draws (if any), use of records, time required, and setting/location. If it is available: Upload a study flow sheet or table to **Zipline**.

For studies comparing standards of care: It is important to accurately identify the research procedures. See UW IRB [POLICY](#) [Risks of Harm from Standard Care](#) and the draft guidance from the federal Office of Human Research Protections, ["Guidance on Disclosing Reasonably Foreseeable Risks in Research Evaluating Standards of Care"](#); October 20, 2014.

Information about pediatric blood volume and frequency of draws that would qualify for expedited review can be found in this [reference table](#) on the Seattle Children's IRB website.

T0 BASELINE ASSESSMENT

Consent/Accent

Eligible participants will be contacted by the study team to schedule a data collection session, either at participant homes or convenient quiet location such as a community library. Once scheduled, the study team will email a copy of the consent form for review. IF REQUIRED (temporary) - 24 hours prior to any data collection session, participants will be sent a COVID-19 screening attestation. At the T0 session, the study team will describe the purpose of the study and obtain informed consent from the parent by iPad via the REDCap e-consent module (consenting for parent and child both to participate). The consent will include the optional cognitive battery for an additional \$25 per timepoint. Parents will receive an automated emailed PDF copy of their consent form after completion. After this, child assent will be obtained – a recording from the PI will be played via iPad. If the recording does not function, the study team will read the assent materials to the child. The child will indicate whether they agree or disagree via REDCap (green check mark and “Yes, I’ll join the study or red ‘x’ and “no, I do not want to join the study”).

Data collection

Following consent and assent, the study team member will perform the direct child measures (height and weight). Next, the study team will assist the parent with pairing the spirometer with their phone. Note, to calculate

expected lung functioning, spirometers use a reference database that requires patient details including age, gender, height, weight. The parent will be instructed to input the study # (instead of name), year of birth (not date) to avoid unnecessary PHI disclosure. The study team will coach the child through spirometry and request that the results be sent to the study team (via email or text). Note, study team will make every effort to perform spirometry outside (weather permitting) and remain socially distanced and advised to wear masks for spirometry, since it is considered an aerosolizing procedure.

Next, individual data collection will commence. Parent participants will be provided an iPad with the electronic instruments preloaded and instructed to complete the instruments to the best of their ability. If questions arise, the study team will answer as needed. The study team will then work 1:1 with the child and assist with instrument completion (reading items, if requested). This technique has been used successfully in [name] other prior dyadic study designs to preclude parental interference in child items. Full instrument descriptions and timepoints are outlined in table below. Estimated time burden: Parent: 50-55 minutes; Child: 40-50 (plus 30-40 if cognitives added).

Assignment

REDCap randomization module will be used to assign dyads to groups using an externally generated block randomization scheme (stratified by sex). After surveys are complete, the study team will assign dyads to intervention or control by selecting “randomize” within REDCap and proceeding with the following, depending on assignment:

Control

Dyads assigned to the usual care control group will be advised of their assignment. An information sheet will be provided that outlines the upcoming data collection sessions (T1 at 8 weeks and T2 and 16 weeks) with compensation amounts. They will be advised to keep the spirometer to use in future visits, and more frequently if they choose. The PI will send the parent an asthma control assessment, based upon spirometry and asthma status questions (C-ACT), with interpretation using the national asthma guideline standards. This report may be shared with the child's health care provider, if desired. Finally, the family will be advised that at the end of the 16 week study period, they will be offered access to the IMPACT system, including the app and wearable device, should they wish to use it.

Intervention

Dyads assigned to the intervention group will be advised of their assignment. An information sheet will be provided that outlines the intervention tasks (weekly activities) as well as upcoming data collection sessions and compensation amounts. Next, the study team will assist the parent with accessing/downloading the IMPACT app. The family will be encouraged to follow the onboarding screens once downloaded, including pairing the app with the event marker watch (symptom watch) and spirometer device. The symptom watch is a commercially available event marker button that resembles a wristwatch. Children will be taught to press the button when asthma symptoms occur. These events are stored by the watch and synced with the app when connected to the parent phone's Bluetooth.

IMPACT intervention overview:

- Families will be asked to check in on the child's asthma daily (they may use the app to set SMS notifications, if desired) to review symptoms reported by the watch (tracked in the app dashboard).
- They will also be asked to log in weekly to select asthma shared management goals (provided), anticipated barriers, and problem solving. Each subsequent week, dyads will report on their goal progress and select new goals or retain the previous ones.
- To monitor asthma control, families will be prompted to complete the C-ACT (7 item questionnaire) and for the child to complete spirometry. C-ACT and spirometry scores are tracked in the app dashboard (see image)

- The intervention concludes after 8 weeks. The app is configured such that after the 8-week intervention, the goal-setting/monitoring feature is “muted”, but dyads may continue to use the monitoring features (medication use, symptoms, asthma control).

T1 POST-INTERVENTION ASSESSMENT (8 WEEK)

The study team will schedule the T1 data collection session at week 8. The child will be asked to complete spirometry and export results to the study team, as in T0. Dyads will be asked to complete parent and child instruments outlined in the table below, again using the iPads as described above. Families assigned to the intervention will complete short intervention questionnaires and a brief semi-structured interview. Parent: 65-75 minutes; Child: 60-75 (plus 30-40 if cognitives added).

T2 FOLLOW-UP ASSESSMENT (16 WEEKS)

T2 data collection is nearly identical to week 8, with children performing spirometry followed by parents and children individually completing iPad instruments. Intervention families will be advised that they may continue using the app if they are interested, though study involvement has concluded (app will remain active). Control families will be given the option to access the app. For those interested, the study team will assist with app download and setup as described in T0. Estimated time burden: Parent: 45-50 minutes; Child: 40-50 (plus 30-40 if cognitives added).

This study requires in person sessions for data integrity and to facilitate participant use of new technologies (app, spirometer, symptom watches). Should the COVID-19 situation evolve, the following remote protocol will be used. Additionally, cognitive measures may only be collected in person.

Remote protocol (due to COVID-19 restrictions or participant family preference)

Remote protocol (if needed): Should remote study visits be required or preferred by participants, the study team will mail study materials (spirometer, paper tape measure) and arrange for web conferencing sessions via Zoom. A link to the study e-Consent and assent form (with video of the PI reading the assent script) will be sent at that time. Families may complete consent and assent asynchronously. If not completed prior to the web conference, the study team will display the REDCap e-Consent module using screen share and allow the parent time to review and complete. Once completed, the study team will read the study assent to the child. After consent and assent, the parent will be sent a personalized weblink to their visit surveys via REDCap. For child survey data – the study personnel will display the surveys using screen share during the web conference. The child may either use “mouse control” to self-select their responses or verbally indicate their responses and study personnel will enter them. Next, the study team member will assist dyads with connecting the previously mailed spirometer to the parent’s smart phone via Bluetooth and mobile app. The app automatically prompts the user to enter sex at birth, age, height (paper tape measure provided) and weight (based upon recall). The family will be instructed to enter the child’s participant ID in the “name” field. The dyad will follow the app instructions for performing spirometry. The final spirometry report will be emailed to the study email. After baseline measures, dyads will be assigned either to the intervention or control group. For those assigned to the intervention group, the study personnel will remotely assist intervention dyads with downloading IMPACT, pairing the symptom watch and reader with app, and reviewing written instructions for use. For dyads assigned to the control arm, they will keep the spirometer for future study sessions.

Future data collection sessions will use a similar Zoom protocol. Note, optional cognitive evaluations are only available in person.

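### After allocation, unmasked study staff work one-to-one with the child on the child-reported primary outcomes, so staff expectation could favour IMPACT; the size cannot be estimated

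*Protocol*

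**What the plan says.** **T0 (Protocol 5.1, Data collection and Assignment).** The parent completes instruments alone on an iPad, with staff available for questions. For the child: "The study team will then work 1:1 with the child and assist with instrument completion (reading items, if requested". The stated reason for this method is to keep parents from influencing child answers. Allocation comes next: "After surveys are complete, the study team will assign dyads to intervention or control by selecting" the randomise button in REDCap. The team then tells the dyad its arm and helps intervention families set up the app, watch and spirometer.

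**T1 (5.1).** "Dyads will be asked to complete parent and child instruments outlined in the table below, again using the iPads as described above". Intervention families also complete short IMPACT questionnaires and an interview.

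**T2 (5.1).** "T2 data collection is nearly identical to week 8, with children performing spirometry followed by parents and children individually completing iPad instruments".

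**Remote visits (5.1).** Staff show the child's surveys by screen share. The child either selects answers by mouse control or may "verbally indicate their responses and study personnel will enter them". For later visits: "Future data collection sessions will use a similar Zoom protocol". Remote visits are open to families who prefer them or live outside the three counties (2.2, 4.6), so they are not only a pandemic fallback.

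**Staffing and blinding.** Section 8.2 names the visit team as PI and student assistant. Section 12.3 gives both of them study procedures and describes no separate assessor. Section 10.7 blinds the statistician and nobody else.

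**Outcomes.** Responsibility and self-efficacy are primary (1.5). Both have parent and child versions on 5-point scales (5.4 table). The AIM also has a child version and is given at T1 to the intervention arm only. The SAP sets an acceptability benchmark of at least 60% of participants scoring 4 or 5.

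**The concern.** Children aged 7 to 11 answer subjective items with an adult beside them, or on screen with them, who may read the items and sometimes enters the answers. After allocation, that adult belongs to the small team that assigned the dyad and set up the app. Section 1.8 says this team co-designed IMPACT, and the SAP predicts larger gains in the intervention arm. Tone, prompting or the interpretation of a hesitant spoken answer could move intervention children's scores in the predicted direction.

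The trial's efficacy product is a set of preliminary effect sizes (1.5). Any such shift adds directly to them and would pass into the planning of a larger trial. Child post-test scores also enter the dyadic model in the SAP.

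The child AIM raises a different problem. A child may rate the app kindly because the people who brought it are present.

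**Working it through.** The documents contain no power, alpha or effect-size calculation, so there is no plan figure to reproduce. The main check is to set the passages side by side; the arithmetic afterwards is illustrative only.

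**1. Is the arm known when outcomes are taken?** At T0, no: surveys precede randomisation. At T1 and T2, the documents do not say in words that the person helping the child knows the arm, but the inference is strong:
- the team is small and does the assigning and onboarding itself;
- at T1 the IMPACT questionnaires and interview go to one arm only;
- at T2 staff tell intervention families they may keep the app and offer control families access;
- no masking step is described for anyone except the statistician.

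**2. Does the one-to-one method apply after allocation?** Yes, by cross-reference. T1 proceeds "again using the iPads as described above", T2 is described as nearly the same, and later remote sessions follow a similar protocol.

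**3. Can baseline adjustment remove it?** No. The T0 score is taken before allocation. If staff influence adds b to intervention children's follow-up scores, the baseline-adjusted difference has expectation (true effect + b).

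**4. What would an assumed shift do?** Assumptions, none stated in the documents: 1:1 allocation of 60 dyads (30 per arm), or 30 × 0.80 = 24 per arm at the SAP's 80% retention benchmark; two-sided alpha 0.05; unadjusted comparison of means; no true effect; shift of b SD.

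SE = √(2/n), and P(significant) = Φ(b/SE − 1.96) + Φ(−b/SE − 1.96).

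For b = 0.3, n = 30: SE = √(2/30) = 0.258; b/SE = 1.162; Φ(−0.798) = 0.2124; the other tail adds 0.0009; total 0.213.

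| Assumed shift (SD) | 30 per arm | 24 per arm |
|---|---|---|
| 0 | 5% | 5% |
| 0.1 | 7% | 6% |
| 0.2 | 12% | 11% |
| 0.3 | 21% | 18% |
| 0.5 | 49% | 41% |

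The SAP's baseline-adjusted comparison would have a smaller standard error, so the same shift would matter somewhat more.

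**5. AIM benchmark.** Assume one rating per dyad. Passing needs 0.60 × 30 = 18 of 30, or 0.60 × 24 = 14.4, hence 15 of 24. The chance of passing is the binomial upper tail.

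| Probability of a 4 or 5 | 30 raters | 24 raters |
|---|---|---|
| 50% | 18% | 15% |
| 60% | 58% | 49% |
| 70% | 92% | 85% |

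If true acceptability were 50%, courtesy that lifted ratings to 70% would turn a likely fail into a likely pass. In practice the benchmark pools parents and children, so courtesy among children alone would move it less.

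**The case against.** Several points on the other side stand and limit the claim.

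- **Staff control is partial.** Items are read only on request. The T2 text has children completing instruments individually. Staff entry at remote visits is one of two options. A reader might infer that staff routinely read the items and enter the answers; the documents do not say so.
- **Baseline is clean.** A reader who takes the T0 sentence alone might infer unmasked administration throughout. At T0 no arm exists yet.
- **Parent versions are less exposed.** Parents answer both primary instruments themselves.
- **Some protection exists.** Section 10.1 has subjects told that there are no right answers. Section 12.4 mentions procedure manuals, checklists and monitoring of student assistants. The manuals are not in the documents, so they may hold a neutral reading rule. The protocol itself states none, and no self-entry rule.
- **The one-to-one method answers a real competing bias**, parental interference, and should stay.
- **AIM is not a masking problem.** A reader might infer that staff knowledge of the arm biases AIM. There is no control-arm AIM, so only courtesy bias applies, and masking to arm could not cure it.
- **Order of instruments.** A reader might infer that the IMPACT interview contaminates the two-arm outcomes. Both the T1 text and the 5.4 table list the IMPACT-only items last.
- **This is an unmaskable behavioural pilot.** Families know their arm, and their own expectations will affect self-report whatever staff do. That bounds what a fix can achieve, but it does not justify leaving an avoidable staff contribution in place.

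**Conclusion.** The concern holds in limited form. At T1 and T2, staff who very probably know the arm assist with the child-reported primary outcomes, and no masking or standard administration rule is stated for them. A shift in favour of IMPACT is possible and could not be removed by baseline adjustment. Separately, the child AIM is open to courtesy bias.

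The documents do not give the size or prove the direction. The false-positive and benchmark figures rest on assumed shifts, equal allocation and, for AIM, one rating per dyad. A reader might infer that the bias is as large as the treatment effect. That is unsupported, because no expected effect, SD or size of staff influence is stated anywhere. The change is worth making because it is cheap and the trial already has the tools, not because a large bias has been shown.

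**What to change.** **At T0, T1 and T2 alike:**
- Make child self-entry the default, by tapping the iPad or by mouse control.
- Present items through the same recorded audio, or a fixed script read verbatim. The trial already does something similar for assent: "a recording from the PI will be played via iPad".
- Limit staff to device help and neutral prompts.
- Allow staff entry only when the child cannot self-enter. Record the administration mode at each visit and run a sensitivity analysis by mode. With 60 dyads, and mode partly chosen by families, this will be descriptive.

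The change must cover all three visits. Applying it only at T1 and T2 would alter the mode between baseline and follow-up and weaken the baseline adjustment.

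**At T1 and T2:** where two team members are available, the one who did not do that dyad's assignment and app set-up runs the child session. State explicitly that two-arm instruments come before IMPACT-only items; this only confirms the order already listed.

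**AIM:** have the child self-enter it without staff viewing the answers.

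**Reporting:** state that outcome staff were not masked and that families knew their arm.

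**Cost:** no extra staff, but recording and REDCap set-up, a procedure-manual change, slightly less flexible help for weak readers, and possibly an IRB modification. From the 5.4 table the child items number 10 + 8 + 10 + 12 + 10 + 4 + 13 + 8 = 75. If recording all of them is too much, record the two primary instruments (10 + 12 = 22 items) and use the verbatim script for the rest.
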